APPENDIX 3. IDENTIFICATION OF SUICIDALITY, HOMICIDALITY, AND/OR RISK OF HARM TO SELF OR OTHERS

Condition	Data Source	Criteria
Suicidality or Risk of Harm to Self	Adverse events	
 • AEs with preferred term of “Completed suicide” or “Suicide attempt” • Medical review of all AEs contained in the MedDRA SMQ of “Suicide/self-injury (SMQ)”
	C-SSRS	
 • C-SSRS findings of at least one occurrence of suicidal ideation (Item 4 and/or Item 5) or at least one occurrence of suicidal behavior • C-SSRS findings of self-injurious behavior, defined as a “Yes” answer to the following question in the Suicidal Behavior section: Has subject engaged in Non-Suicidal Self-Injurious behavior?
Homicidality or Risk of Harm to Others	Adverse events	
 • AEs with preferred term of “Aggression”, “Anger”, “Antisocial behaviour”, “Belligerence”, “Defiant behaviour”, “Homicide”, “Homicidal Ideation”, “Hostility”, “Physical abuse”, “Physical assault”, or “Violence-related symptom” contained in the MedDRA SMQ of “Hostility/aggression (SMQ)” • AEs with a verbatim term that contains text of “homicid*”, “kill*”, or “murder*”.

Document: Documentation\SAP

Author:

Version Number:

Final V1.0

Version Date:

27FEB2019

Template No: CS_TP_BS016 Revision 4
 Effective Date: 01Apr2016

Reference: CS_WI_BS005

Copyright © 2009, 2010, 2012, 2016 Quintiles Transnational Corp. All rights reserved.

The contents of this document are confidential and proprietary to Quintiles Transnational Corp. Unauthorized use, disclosure or reproduction is strictly prohibited.

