6.2. Secondary Endpoints

- Absolute values and changes from double-blind (DB) Baseline of Study SEP361-201 and open-label (OL) Baseline of Study SEP361-202 in clinical laboratory tests (hematology, serum chemistry, urinalysis, glucose and lipid panel, prolactin, glycosylated hemoglobin (HbA_{1c}))
- Absolute values and changes from DB Baseline of Study SEP361-201 and OL Baseline of Study SEP361-202 in clinical evaluations (vital signs body weight, BMI, blood pressure [supine and standing], heart rate [supine and standing], 12-lead ECGs)
- Frequency and severity of suicidal ideation and suicidal behavior using the C-SSRS
- Rate of relapse and time to relapse during the 26-week OL period for subjects who demonstrated a clinical response to 4 weeks of treatment with SEP-363856. Relapse will be defined as the onset of any of the following:
 - An increase in PANSS total score $\geq 30\%$ from the PANSS total score at clinical response and a CGI-S score ≥ 3
 - Re-hospitalization for worsening of psychosis
 - Emergence of suicidal ideation, homicidal ideation and/or risk of harm to self or others.
- Changes from DB Baseline of Study SEP361-201 and OL Baseline of Study SEP361-202 in PANSS total score and subscale scores (positive, negative, and general psychopathology)
- Change from DB Baseline of Study SEP361-201 and OL Baseline of Study SEP361-202 in CGI-S score.
- Change from DB Baseline of Study SEP361-201 and OL Baseline of Study SEP361-202 in BNSS total score.
- Change from DB Baseline of Study SEP361-201 and OL Baseline of Study SEP361-202 in MADRS total score.
- Proportion of subjects who achieve a response, defined as a 20% or greater improvement in PANSS total score from the baseline, and calculated using (1) the DB Baseline of Study SEP361-201 for subjects assigned to double-blind SEP-363856, and (2) the OL Baseline of Study SEP361-202 for subjects assigned to double-blind placebo.

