16.2.6. RATE OF RELAPSE AND TIME TO RELAPSE

Subjects demonstrating a relapse of psychotic symptoms during the OL extension treatment period will be identified on the relapse population.

Relapse is defined as the earliest occurrence of any of the following:

- An increase in PANSS total score by $\geq 30\%$ from the PANSS total score at clinical response and a CGI-S score ≥ 3

Document: Documentation\SAP

Author:

Version Number:

Final V1.0

Version Date:

27FEB2019

Template No: CS_TP_BS016 Revision 4
 Effective Date: 01Apr2016

Reference: CS_WI_BS005

Copyright © 2009, 2010, 2012, 2016 Quintiles Transnational Corp. All rights reserved.

The contents of this document are confidential and proprietary to Quintiles Transnational Corp. Unauthorized use, disclosure or reproduction is strictly prohibited.

- Re-hospitalization for worsening of psychosis
- Emergence of suicidality, homicidality, and/or risk of harm to self or others

PANSS and CGI-S assessments taken at both scheduled and unscheduled visits will be considered when identifying the relapse event. Occurrence of re-hospitalization for worsening of psychosis will be identified by medical review of the data collected on the Psychiatric Hospitalization CRF page as well as the SAEs prior to database lock. Emergence of suicidality, homicidality, and/or risk of harm to self or others will be identified as outlined in Appendix 3. The evaluation period for relapse will be from the day/time of clinical response to 1 day after the day of the last dose of extension study medication.

The date of relapse is defined as the earliest of: the date of the assessment (based on the QSSTDTC variable in Bracket data) at which the qualifying PANSS and CGI-S data were collected, the date of hospital admission for worsening of psychosis, the date of the assessment (based on the QSSTDTC variable in Bracket data) at which a qualifying C-SSRS event is identified, or the start date of the qualifying adverse event.

The date of clinical response is defined as the date of the PANSS and CGI-S assessments (based on the QSSTDTC variable in Bracket data) which established clinical response.

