Time-to-relapse (in days) is defined as the date of relapse – the date of clinical response + 1. Subjects completing/discontinuing from the study without meeting the criteria for relapse will be censored on the day after the last dose of extension study medication. Kaplan-Meier estimates of the median time-to-relapse and the 25th percentile and 75th percentile of time-to-relapse, along with the respective 95% confidence intervals, will be calculated. Kaplan-Meier estimate of the probability of relapse at the end of the OL extension treatment period, and its 95% confidence interval, will also be calculated. The time-to-relapse data will be presented in a Kaplan-Meier curve.

The rate of relapse will be calculated as the proportion of subjects demonstrating a relapse during the OL extension treatment period in the relapse population. The 95% confidence interval for the rate of relapse will also be calculated.

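### Does counting every adverse event coded to anger, belligerence or defiance as a relapse call for an extra relapse analysis?

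*SAP*

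**What the plan says.** The third relapse criterion in protocol section 6.2 is "Emergence of suicidal ideation, homicidal ideation and/or risk of harm to self or others". SAP section 3.7 widens ideation to suicidality and homicidality so that behaviour is covered too, and points to the search criteria in Appendix 3. SAP section 16.2.6 then sets the rule: "Relapse is defined as the earliest occurrence of any of the following". The relapse date for this route is "or the start date of the qualifying adverse event".

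Appendix 3 has two rows:

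- **Self-harm.** Two adverse event terms (completed suicide, suicide attempt) count automatically. The rest go through "Medical review of all AEs contained in the MedDRA SMQ of" suicide and self-injury. From the C-SSRS, ideation at Item 4 or 5, any suicidal behaviour and non-suicidal self-injury also count automatically.
- **Harm to others.** Adverse events are the only source. The row opens with "AEs with preferred term of “Aggression”, “Anger”, “Antisocial behaviour”, “Belligerence”, “Defiant behaviour" and lists 11 terms in all. It adds "AEs with a verbatim term that contains text of" any of three strings (homicid*, kill*, murder*). It sets no severity or review condition.

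For the hospital criterion, section 16.2.6 says "Occurrence of re-hospitalization for worsening of psychosis will be identified by medical review of the data collected on the Psychiatric Hospitalization CRF page", together with the serious adverse events. The relapse rate is "the proportion of subjects demonstrating a relapse during the OL extension treatment period in the relapse population", with a 95% confidence interval. The other relapse outputs named are Kaplan-Meier quartiles, the end-of-period probability and the curve.

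**The concern.** Anger, belligerence and defiance need not show homicidality or a risk of harm to anyone. Protocol section 12.3 allows an adverse event to be mild, meaning that it is usually transient and leaves daily activities unaffected. Such an event, if it falls between clinical response and one day after the last dose, would still be a relapse in a responder.

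The other routes look better guarded. PANSS worsening needs a rise of at least 30% together with a CGI-S score of at least 3. Re-hospitalization is reviewed medically, and so are most adverse events in the self-harm row.

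Relapse rate and time to relapse are the only measures named for the objective on maintenance of response (protocol section 5.2). If unspecific events entered the count, both could be misstated. The SAP text plans no table by criterion that would show how much of the result came this way.

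**Working it through.** The documents give no relapse figure to reproduce. The check therefore has a textual part and an illustration.

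**1. The rule as written.** Harm-to-others row: 11 preferred terms, 3 text strings, 0 conditions on severity, context or review. Relapse counts by criterion mentioned in SAP 16.2.6: 0. Relapse sensitivity analyses: 0. The description of the text is accurate.

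**2. When a listed event changes the result.**

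| Position of the listed event | Relapse rate | Time to relapse |
|---|---|---|
| After another qualifying event | no change | no change |
| Before another qualifying event | no change | earlier |
| Only qualifying event | one more relapse | event instead of censoring |

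Only the last row alters the rate.

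**3. What the planned outputs show.** SAP 17.1.1 tabulates adverse events by preferred term, and 17.1.1.1 by worst severity within preferred term. These cover the whole safety population, up to 9 days after the last dose. Relapse covers responders, up to 1 day after it. For the 11 terms, the tables therefore give in practice an upper limit on the subjects affected, and show how many had nothing worse than a mild event. They do not cover the text-string route. The listings in 17.1 do: they hold all SEP361-202 adverse events for each subject, and SAP Appendix 1 sorts listings by treatment, subject and date. The text does not say that listings flag responders or the criterion met, so a reader would have to link records.

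**4. Illustration.** Inputs: about 180 subjects (protocol 15.1). The responder share (30%, 50%, 70%), a base relapse rate near 10% and three added subjects are assumptions. Intervals are Clopper-Pearson, also assumed, because the SAP names no method.

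- Responders: 0.30 × 180 = 54; 0.50 × 180 = 90; 0.70 × 180 = 126.
- Each added relapse: 100/54 = 1.85, 100/90 = 1.11, 100/126 = 0.79 percentage points.

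| Responders | Without | With three added |
|---|---|---|
| 54 | 5/54 = 9.3% (3.1 to 20.3) | 8/54 = 14.8% (6.6 to 27.1) |
| 90 | 9/90 = 10.0% (4.7 to 18.1) | 12/90 = 13.3% (7.1 to 22.1) |
| 126 | 13/126 = 10.3% (5.6 to 17.0) | 16/126 = 12.7% (7.4 to 19.8) |

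In each row the shifted estimate stays inside the unshifted interval. With five added at 90 responders, 14/90 = 15.6% (8.8 to 24.7), which is still inside 4.7 to 18.1.

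**The case for a change.** The strongest case for acting accepts the list as the main analysis and asks only for more output: relapses by qualifying criterion, and a sensitivity analysis in which harm-to-others events count only after a review made before lock, without knowledge of the rating-scale results or of treatment in SEP361-201. The cost would be a few lines and one or two tables. Protocol 15.3.11 rules out sensitivity analyses, but the SAP already adds one for BNSS and analyses Cogstate data with and without integrity failures. An effect of unknown size is itself a reason to display it.

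Part of this stands. The two rows of Appendix 3 are treated differently, section 3.7 does not explain why anger or defiance alone should qualify, and a table by criterion would be useful.

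The rest does not carry a change:

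- SAP section 8 says that the templates define the content of tables and listings. They may already contain the count by criterion, so the omission cannot be established.
- A review would bring judgement into an open-label study, where protocol 15.3.6.8 calls for programmatic identification.
- Dropping selected terms needs a reason to remove *Anger* while keeping *Hostility* or *Antisocial behaviour*, and the documents supply none. They do not say which reported events would be coded to each term.
- The BNSS and Cogstate analyses respond to invalid ratings and failed test integrity. Here there is no data fault, only a different preference about breadth.

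**Conclusion.** No change to the plan follows. The rule is broad, but it is written down, reproducible and consistent with the protocol. Protocol section 4.4 excludes hypothesis tests, and section 5.2 calls the maintenance objective exploratory, so no error rate or formal comparison depends on the list. The likely direction is more and earlier relapse, which works against the drug. The main relapse rate and Kaplan-Meier results would be the same with or without the extra output.

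The possible effect is 0.79 to 1.85 percentage points for each subject whose only qualifying event is a listed one, if 30% to 70% of about 180 subjects respond. How many such subjects there will be cannot be known from the documents. If there are few, the shift is small against the width of the interval. If there are many, the tables by preferred term and severity will show that the listed terms are common, and the listings allow it to be traced. Anyone who holds the templates can check whether relapse is split by criterion. Adding that split would be a convenience, and the sensitivity analysis is a matter of preference on which reasonable statisticians differ.

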APPENDIX 4. PSQI SCORING SHEET

Source: <http://www.sleep.pitt.edu/research/instruments.html>

Document: Documentation\SAP

Author:

Version Number:
Version Date:

Final V1.0
27FEB2019

Template No: CS_TP_BS016 Revision 4
Effective Date: 01Apr2016

Reference: CS_WI_BS005

Pittsburgh Sleep Quality Index (PSQI)

Form Administration Instructions, References, and Scoring

Form Administration Instructions

The range of values for questions 5 through 10 are all 0 to 3.

Questions 1 through 9 are not allowed to be missing except as noted below. If these questions are missing then any scores calculated using missing questions are also missing. Thus it is important to make sure that all questions 1 through 9 have been answered.

In the event that a range is given for an answer (for example, '30 to 60' is written as the answer to Q2, minutes to fall asleep), split the difference and enter 45.

Reference

Scores – reportable in publications

On May 20, 2005, on the instruction of [name], the scoring of the PSQI was changed to set the score for Q5J to 0 if either the comment or the value was missing. This may reduce the DISTB score by 1 point and the PSQI Total Score by 1 point.

PSQIDURAT

DURATION OF SLEEP

IF $Q4 \geq 7$, THEN set value to 0
 IF $Q4 < 7$ and ≥ 6 , THEN set value to 1
 IF $Q4 < 6$ and ≥ 5 , THEN set value to 2
 IF $Q4 < 5$, THEN set value to 3
 Minimum Score = 0 (better); Maximum Score = 3 (worse)

PSQIDISTB

SLEEP DISTURBANCE

IF $Q5b + Q5c + Q5d + Q5e + Q5f + Q5g + Q5h + Q5i + Q5j$ (IF Q5JCOM is null or Q5j is null, set the value of Q5j to 0) = 0, THEN set value to 0

IF $Q5b + Q5c + Q5d + Q5e + Q5f + Q5g + Q5h + Q5i + Q5j$ (IF Q5JCOM is null or Q5j is null, set the value of Q5j to 0) ≥ 1 and ≤ 9 , THEN set value to 1

IF $Q5b + Q5c + Q5d + Q5e + Q5f + Q5g + Q5h + Q5i + Q5j$ (IF Q5JCOM is null or Q5j is null, set the value of Q5j to 0) > 9 and ≤ 18 , THEN set value to 2

IF $Q5b + Q5c + Q5d + Q5e + Q5f + Q5g + Q5h + Q5i + Q5j$ (IF Q5JCOM is null or Q5j is null, set the value of Q5j to 0) > 18 , THEN set value to 3

Minimum Score = 0 (better); Maximum Score = 3 (worse)

Document: Documentation\SAP

Author:

Version Number:

Final V1.0

Version Date:

27FEB2019

Template No: CS_TP_BS016 Revision 4
 Effective Date: 01Apr2016

Reference: CS_WI_BS005

PSQILATEN

SLEEP LATENCY

First, recode Q2 into Q2new thusly:

IF Q2 \geq 0 and \leq 15, THEN set value of Q2new to 0
 IF Q2 $>$ 15 and \leq 30, THEN set value of Q2new to 1
 IF Q2 $>$ 30 and \leq 60, THEN set value of Q2new to 2
 IF Q2 $>$ 60, THEN set value of Q2new to 3

Next

IF Q5a + Q2new = 0, THEN set value to 0
 IF Q5a + Q2new \geq 1 and \leq 2, THEN set value to 1
 IF Q5a + Q2new \geq 3 and \leq 4, THEN set value to 2
 IF Q5a + Q2new \geq 5 and \leq 6, THEN set value to 3

Minimum Score = 0 (better); Maximum Score = 3 (worse)

PSQIDAYDYS

DAY DYSFUNCTION DUE TO SLEEPINESS

IF Q8 + Q9 = 0, THEN set value to 0
 IF Q8 + Q9 \geq 1 and \leq 2, THEN set value to 1
 IF Q8 + Q9 \geq 3 and \leq 4, THEN set value to 2
 IF Q8 + Q9 \geq 5 and \leq 6, THEN set value to 3
 Minimum Score = 0 (better); Maximum Score = 3 (worse)

PSQIHSE

SLEEP EFFICIENCY

Diffsec = Difference in seconds between day and time of day Q1 and day Q3
 Diffhour = Absolute value of diffsec / 3600
 newtib = IF diffhour $>$ 24, then newtib = diffhour - 24
 IF diffhour \leq 24, THEN newtib = diffhour
 (NOTE, THE ABOVE JUST CALCULATES THE HOURS BETWEEN GNT (Q1) AND
 GMT (Q3))
 tmpmse = (Q4 / newtib) * 100

IF tmpmse \geq 85, THEN set value to 0
 IF tmpmse $<$ 85 and \geq 75, THEN set value to 1
 IF tmpmse $<$ 75 and \geq 65, THEN set value to 2
 IF tmpmse $<$ 65, THEN set value to 3
 Minimum Score = 0 (better); Maximum Score = 3 (worse)

PSQISLPQUAL

OVERALL SLEEP QUALITY

Q6
 Minimum Score = 0 (better); Maximum Score = 3 (worse)

PSQIMEDS

NEED MEDS TO SLEEP

Q7
 Minimum Score = 0 (better); Maximum Score = 3 (worse)

PSQI

TOTAL

DURAT + DISTB + LATEN + DAYDYS + HSE + SLPQUAL + MEDS
 Minimum Score = 0 (better); Maximum Score = 21 (worse)

Document: Documentation\SAP

Author:

Version Number:
 Version Date:

Final V1.0
 27FEB2019

Template No: CS_TP_BS016 Revision 4
 Effective Date: 01Apr2016

Reference: CS_WI_BS005

Interpretation: TOTAL ≤ 5 associated with good sleep quality
 TOTAL > 5 associated with poor sleep quality

APPENDIX 5. UPSA-B SUMMARY SCORING

UPSA-B SUMMARY SCORING:

Upon completion of the UPSA-B, scores are assigned for each of the 2 subscales. Points achieved for each subscale are summed and entered into the appropriate boxes in column 2 of the scoring worksheet. Subscale scores (column 6) are calculated using the formulae provided in columns 3, 4, and 5 of the worksheet. Fraction scores in column 6 are rounded to the nearest interval, whereby a score of 3.1 would be rounded to 3, and 3.51 would be rounded to 4). An UPSA-B Total Score (range = 0-100) is entered at the bottom of the worksheet by summing the subscales scores in column 6. See sample scoring worksheet calculations below. A blank summary scoring worksheet is provided on page 14.

UPSA-B “Sample” Summary Scoring Worksheet

1.	2.	3.	4.	5.	6.
Domain	Total Score	÷	Percent Correct	x 50	Subscale Score
Financial	5	÷ 11 =	.45	x 50 =	23
Communication	4	÷ 9 =	.44	x 50 =	22
UPSA-B Total Score (Range = 0-100)					45
